## Protocol for non-interventional studies based on existing data

Document Number:	c18071759-01
BI Study Number:	1321-0022
BI Investigational Product(s):	Prazaxa (Dabigatran etexilate)
Title:	Medical Need of Non-vitamin K Oral Anti-coagulant Reversal in Japan: Epidemiological Assessment of Emergency Surgery, Major Bleeding due to Trauma and Fracture, using Large Scale Claims Database
Protocol version identifier:	Version 1.0
Date of last version of protocol:	Not Applicable
PASS:	No
EU PAS register number:	Not Applicable
Active substance:	Dabigatran, warfarin, apixaban, rivaroxaban, edoxaban
Medicinal product:	Dabigatran, warfarin, apixaban, rivaroxaban, edoxaban
Product reference:	Not applicable
Procedure number:	Not Applicable
Joint PASS:	No
Research question and objectives:	The primary objective of this study is to assess, for adult patients initiating an oral anticoagulant for non-valvular atrial fibrillation, the incidence rates of emergency surgery, major bleeding due to fracture, and major bleeding due to trauma, overall and stratified by age (<64, 65-74, >75). The secondary objective of the study is to assess the incidence rates of cardiac tamponade or pericardiocentesis, overall and stratified by age (<64, 65-74, >75). .
Country(-ies) of study:	Japan

Author:	
Marketing authorisation holder(s):	
MAH contact person:	
In case of PASS, add: <EU-QPPV:>	Not Applicable
In case of PASS, add: <Signature of EU-QPPV:>	Not Applicable
Date:	18 July 2017

**2. LIST OF ABBREVIATIONS**

ACE	Angiotensin Converting Enzyme inhibitors
AF	Atrial Fibrillation
ARB	Angiotensin Receptor Blockers
ATC	Anatomical Therapeutic Chemical
CCB	Calcium-Channel Blocker
DPC	Diagnosis Procedure Combination
ICD	International Classification of Diseases
MDV	Medical Data Vision
NOAC	Non-warfarin Oral Anti Coagulants
NVAF	Non-Valvular Atrial Fibrillation
OAC	Oral Anticoagulants

## 4. ABSTRACT

Name of company: Boehringer Ingelheim			
Name of finished medicinal product: Prazaxa			
Name of active ingredient: Dabigatran etexilate			
Protocol date: 18 July 2017	Study number: 1321-0022	Version/Revision: 1.0	Version/Revision date: Not applicable
Title of study:  Medical Need of Non-vitamin K Oral Anti-coagulant Reversal in Japan: Epidemiological Assessment of Emergency Surgery, Major Bleeding due to Trauma and Fracture, using Large Scale Claims Database			
Rationale and background:  There has been no epidemiological assessment to investigate the medical need of reversal in patients undergoing emergency surgery or major bleeding from trauma or fracture receiving oral anticoagulant in Japan. The objective of this study is to assess the incidence of emergency surgery and major bleeding associated with fracture and head trauma in Japanese patients prescribed with oral anti-coagulants such as warfarin, dabigatran, apixaban, rivaroxaban and edoxaban			
Research question and objectives:  The primary objective is to assess, for adult patients initiating an oral anticoagulant for non-valvular atrial fibrillation (NVAF), the incidence rates of emergency surgery, major bleeding due to trauma, and major bleeding due to fracture, overall and stratified by age (<64, 65-74, >75). The secondary objective is to estimate the overall and age stratified incidence of cardiac tamponade and pericardiocentesis.			
Study design:  Non-interventional study based on existing health insurance claims data			
Population:  Medical Data Vision (MDV) clinical database is used Oral anticoagulants (OAC) naïve, adult patients with NVAF initiating dabigatran, warfarin, apixaban, rivaroxaban or edoxaban between March 1, 2011 and June 30, 2016  Inclusion criteria: patients aged >18 year-old with confirmed diagnosis of NVAF (International Classification of Diseases (ICD) 10 I48), having a first prescription (index date) of any one of OACs (dabigatran, warfarin, rivaroxaban, apixaban or edoxaban) having no prescription of OACs for 6 months prior to the index date (this period is defined as the baseline period).  Exclusion criteria: patients having less than 6 months of enrolment prior to the index date, being dialysis or kidney transplant recipients in baseline period, having either atrial flutter, valvular atrial fibrillation (AF), mechanical valve placement, rheumatic AF, and/or mitral valve prolapse/regurge/stenosis in baseline period, and having record of deep			

Name of company: Boehringer Ingelheim			
Name of finished medicinal product: Prazaxa			
Name of active ingredient: Dabigatran etexilate			
Protocol date: 18 July 2017	Study number: 1321-0022	Version/Revision: 1.0	Version/Revision date: Not applicable
Variables: vein thrombosis or pulmonary embolism < 6months before AF diagnosis in baseline period.			
Data sources:	MDV clinical database. The database is health insurance claims database. As of end of February 2016, MDV has accumulated claims records from 12.94 million patients, both in and out-patients, from more than 230 large acute, sub-acute and outpatient care DPC hospitals.		
Study size:	The previous study 1160.279 has identified the patients with confirmed 6 months of baseline period and no OAC treatment (defining “treatment naïve” new starter population). The total of these patients was 62,888. The breakdown by OAC initiated was 7,441 for dabigatran, 23,412 for warfarin, 16,026 for apixaban, 12,779 for rivaroxaban and 3,230 for edoxaban. The mean on-treatment follow-up duration for all OACs new starters combined in patients with one year of baseline period was calculated as 121 days. The mean on-treatment follow-up duration for all OACs new starters combined with 6 months of baseline period is unknown.		
Data analysis:	Baseline characteristics of patients overall and stratified by age will be provided in a tabulated format.  The main analysis will be on OAC-naïve initiators and will consider outcomes until the complete discontinuation of any OAC (i.e. including the periods during which patients switched from an OAC to another OAC in less than 14 days)		
For the primary objective			

Name of company: Boehringer Ingelheim			
Name of finished medicinal product: Prazaxa			
Name of active ingredient: Dabigatran etexilate			
Protocol date: 18 July 2017	Study number: 1321-0022	Version/Revision: 1.0	Version/Revision date: Not applicable

Incidence rate (overall and age stratified) of emergency surgery, and major bleeding due to fracture, and major bleeding due to trauma will be described with number of patients presenting the event, patient-years and 95% confidence interval overall and stratified by age.
 
For the secondary objective
 
1. Incidence rates (overall and age stratified) of cardiac tamponade or peri-cardiocentesis, along with number of events, patient year of follow-up and 95% confidence interval.
			
Milestones:	
Start of Data Analysis: 1 Aug 2017
 
End of Data Analysis: 19 Sep 2017
 
Study Report: 30 Nov 2017
		

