#### Definition of terminology

1. Index date: the date of first oral anticoagulant prescription, namely dabigatran, apixaban, rivaroxaban, edoxaban and warfarin
2. Follow-up period: the day after index date to the earliest of treatment discontinuation, , end of continuous enrolment in the database, end of study period, first occurrence of the event of interest, or death.
3. Any OAC treatment discontinuation: treatment gap of any one of OACs for more than 14 days including the time after switch from one OAC to another OAC (primary analysis)

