## 9.4 DATA SOURCES

MDV commercial claims database will be used.

Observation period for the primary objective is planned from March 2011 to June 2016 considering the launch date of dabigatran. The observation period for the secondary objective is from March 2008 to June 2016.

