## 9.11 SUBJECTS

The source population is Japanese patients who have claims data in MDV commercial database. In order to have claims in the database, the patients must have received some medical intervention, out or in-patient hospital visit, or pharmacy prescription from the DPC hospitals in Japan. DPC hospitals are large hospitals, often associated with medical schools or government funding, providing both acute and chronic medical care in Japan. Compared to non-DPC hospitals, they tend to provide more specialized, intensive medical care in addition to outpatient primary care tending to chronic disease requiring non-urgent care. MDV database has contractual agreement to receive claims data from approximately 12% of all DPC hospitals in Japan, and the selection is based on the willingness on the side of DPC hospitals to receive either financial compensation or data services from MDV.

The inclusion and exclusion criteria are intended to select those Japanese atrial fibrillation patients who have non-valvular etiology and have newly initiated oral anti-coagulants for stroke prevention. The exclusion criteria also include patients on dialysis or kidney transplant and having records of deep vein thrombosis or pulmonary embolism to exclude those patients who are presumed to have high risk of bleeding and those receiving OAC for indications other than atrial fibrillation.

The data cut-off of 14 Mar 2011 to 30 June 2016 is to select those claims that have occurred after the launch of dabigatran and to the most recent available data cut from MDV at the time of protocol writing.

The availability of co-variates for matching was evaluated in the feasibility analysis of CTMS 1160.279. External validity was assessed by comparing the incidence of claims defined incidence of stroke, intracranial haemorrhage and systemic embolism in MDV database against previously reported prospective atrial fibrillation registry conducted in Japan by Koretsune et al [4]

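### The valvular, flutter, dialysis and transplant exclusions are searched only in the 6 months before the index date, so index-day codes and older records of permanent conditions trigger no exclusion

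*Combined protocol and SAP*

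**What the plan says.** Section 4 (Abstract, Population) is the only place that gives a search window for these exclusions. The renal exclusions and the start of the cardiac list apply to patients "being dialysis or kidney transplant recipients in baseline period, having either atrial flutter, valvular atrial fibrillation (AF), mechanical valve placement". The cardiac list closes with "mechanical valve placement, rheumatic AF, and/or mitral valve prolapse/regurge/stenosis in baseline period". The baseline period is defined through the washout: "having no prescription of OACs for 6 months prior to the index date (this period is defined as the baseline period".

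The definitions in section 9.2 fix the two neighbouring dates:

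- "Index date: the date of first oral anticoagulant prescription"
- "Follow-up period: the day after index date to the earliest of treatment discontinuation"

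Inclusion criterion 4 in section 9.2 makes 6 months of prior enrolment a minimum, not a fixed length. The exclusion list in section 9.2 has three items and contains none of these clinical exclusions. Section 9.11 says that the criteria are meant to "select those Japanese atrial fibrillation patients who have non-valvular etiology", and it repeats the dialysis and transplant exclusion without any time window. Sections 9.9 and 9.12 discuss unvalidated outcome codes and the selection of hospitals. They do not mention eligibility errors that come from the look-back.

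**The concern.** A window that ends the day before the first OAC prescription leaves two gaps.

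- **Index date.** A valve, flutter or renal code first entered on the day the OAC is prescribed lies after the baseline period and before follow-up, so no rule uses it.
- **Older records of permanent conditions.** A mechanical valve stays in place after one procedure, and a transplant may also be visible only through its procedure record. If that record is more than 6 months old and is not repeated, the patient passes the exclusion even where the database holds the record.

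At stake is whether the cohort matches its description as non-valvular AF without dialysis or transplant, and whether the overall and age-specific rates describe that population. Copying the abstract's wording into section 9.2 would carry the same window into the operative list.

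**Working it through.** **1. Time axis on the literal text**

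- 6 months before index: baseline period; exclusions searched (Abstract).
- Index date: in neither the baseline period nor follow-up.
- Day after index onward: follow-up (section 9.2).
- More than 6 months before index: not searched, though enrolment may reach back further (section 9.2, inclusion criterion 4).

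No section states a search that includes the index date or uses all available history.

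**2. Does another rule close the gaps?**

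- *Diagnosis code.* The abstract identifies NVAF by I48, but Table 1 in section 9.3.3 also lists I48 under valvular disease. I48 alone therefore does not establish non-valvular etiology.
- *OAC washout.* In the abstract it covers any OAC, so it removes earlier valve patients whose OAC is recorded in the database. It does not remove those whose OAC was prescribed elsewhere, because section 9.9 says that visits to other institutions are not captured. Exclusion 2 in section 9.2 narrows the washout to the index treatment.
- *Re-coding.* Ongoing dialysis would be expected to recur in claims, unless it is given outside the participating hospitals. A past one-off procedure is less certain to recur. Earlier re-coding does not help when a condition is first coded on the index date.

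The gaps are narrowed but not closed.

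**3. The plan's own figures (section 9.5 and Abstract)**

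- 7,441 + 23,412 + 16,026 + 12,779 + 3,230 = 62,888, as stated.
- 121 / 365.25 = 0.331 year, consistent with the stated value of approximately 0.3 year.

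**4. Illustration of the effect on a pooled rate**

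Let *c* be the share of person-time from patients who should have been excluded, and *RR* their event-rate ratio to the rest. The relative change in the pooled rate is (1 - c) + c·RR - 1 = c·(RR - 1). Neither input is in the documents, so both are assumptions. The patient counts are c × 62,888 and assume equal follow-up.

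| c | patients | RR 0.5 | RR 1.5 | RR 2 | RR 3 |
|---|---|---|---|---|---|
| 1% | 629 | -0.5% | +0.5% | +1% | +2% |
| 2% | 1,258 | -1% | +1% | +2% | +4% |
| 5% | 3,144 | -2.5% | +2.5% | +5% | +10% |
| 10% | 6,289 | -5% | +5% | +10% | +20% |

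**5. Scale against sampling error**

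Person-years: 62,888 × 0.3 = 18,866, or 62,888 × 121/365.25 = 20,834. With exact Poisson 95% intervals and assumed rates:

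- 5 per 1,000 on 18,866 person-years: 94 events, interval 4.03 to 6.10, half-width 20.8% of the rate.
- 20 per 1,000 on 20,834 person-years: 417 events, interval 18.14 to 22.03, half-width 9.7% of the rate.

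The follow-up figure comes from patients with a one-year baseline and omits time after switching. Section 9.5 expects the true mean to be longer, so the real intervals would be narrower at the same rates. On these figures only the upper end of the illustration (c of 5-10% with RR of 2-3) comes near the sampling error.

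**The case against.** Several counter-arguments carry weight.

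- **Status wording.** Being a transplant recipient during baseline can be read as a status, so a transplant years earlier would still count. This stands. The transplant gap exists only if detection relies on a procedure record, and the plan gives no codes that would settle this. Section 9.11 also states the renal exclusion without a window.
- **The washout and recurring claims already catch some patients.** This stands as a reduction of the problem, within the limits shown in the working.
- **A uniform window is a legitimate choice.** Searching all history makes eligibility depend on how long a patient has been in the database. It can also exclude people for old, transient or rule-out codes. This stands for flutter and dialysis, and the fix treats them separately.
- **The main problem is the missing list in section 9.2.** This is true as to order of repair. The window still has to be chosen when the list is restored.

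Three stronger readings are tempting and are not supported.

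- *The rates are inflated by 3-20%.* That range is 0.03 × (2 - 1) to 0.10 × (3 - 1), and neither input comes from the documents. Section 9.11 ties its bleeding-risk rationale to dialysis, transplant and venous thromboembolism, not to flutter or valve disease, so even the direction is open.
- *Look-back of 3.0 to 8.3 years is available.* This counts from March 2008 to the first and last index dates. Section 9.4 says "The observation period for the secondary objective is from March 2008 to June 2016"; for the primary objective the start is March 2011. The figures are calendar maxima, and the history actually held for primary-cohort patients is not stated.
- *Ineligible patients certainly enter the cohort.* Under the abstract's literal rule these patients are eligible. They conflict with the intent in section 9.11, and no passage says how many there are or how often the cause of AF is first coded on the day of the OAC prescription.

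**Conclusion.** The point holds as a gap between the literal search window and the population the protocol says it wants. The index date is searched by no rule, and records older than 6 months of a mechanical valve (or of a transplant, if found by procedure record) are not used. Neither the size nor the direction of the effect on the rates can be derived. The illustrative range of about -5% to +20% rests wholly on assumed contamination of 1-10% and an assumed rate ratio of 0.5-3, and the effect may be negligible. This is a cheap improvement in how well the cohort matches its description, not a demonstrated bias in the results.

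**What to change.** Reconcile the abstract, section 9.2 and section 9.11, and list these exclusions with their codes in section 9.2. In doing so:

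1. For all of them, extend the search window to include the index date. Follow-up starts the next day, so no follow-up information is used.
2. For the permanent conditions (mechanical valve, kidney transplant, rheumatic and mitral valvular disease), search all available records up to and including the index date.
3. Keep the 6-month look-back for the OAC washout and for conditions that may be transient (flutter, dialysis).
4. Report how many patients the wider window additionally excludes, and give the overall and age-stratified rates under the 6-month window as a sensitivity analysis.

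The cost is one change in the selection program, slightly fewer patients, and a look-back for the permanent conditions that varies in length between patients. The last point should be named in section 9.9.

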**5. AMENDMENTS AND UPDATES**

Number	Date	Section of study protocol	Amendment or update	Reason
	None			

**6. MILESTONES**

Milestone	Planned Date
Start of data collection	1 Aug 2017
End of epidemiology analysis	19 Sep 2017
Final report of study results:	30 Nov 2017

## 7. RATIONALE AND BACKGROUND

Until 2002 in Japan, administrative claims data were not standardized or coded electronically. There was limited use for Health Authorities policy decision making or in health research (epidemiological, HTA). Ministry of Health, Labor and Welfare launched the Diagnosis Procedure Combination (DPC) system in 2002 linked with the reimbursement system. DPC is a Japanese version of the Diagnosis Related Groups system; such system is implemented in many countries including UK, US and Germany.

MDV provides commercial claims database consisting of medical records from more than 12.94 million in and out-patients (>80% outpatient claims) from 230 large DPC hospitals as of February 2016.

Dabigatran was the first of the non-warfarin oral anti coagulants (NOACs) to be approved and launched in March 2011 in Japan, then three additional NOACs have been launched for an indication of stroke prevention in patients with non-valvular atrial fibrillation (NVAF). Idarucizumab, a specific reversal agent of dabigatran's coagulation effect, has been launched in November of 2016, and is indicated in dabigatran treated patients who undergo emergency operation or experience life threatening bleeding.

Buchelle et al analysed the German claims database system to calculate the incidence of traumatic brain injury in 65 years or older population, and concluded that 4.8 hospital admissions in 1000 patient year of follow-up, and was found to be higher in nursing home resident with higher morbidity and mortality [1]. Curtis et al reported that fracture annual incidence was 155.3 per 10,000 patient-year in men aged 18-24. For age above 90, the incidence was 224.8 per 10,000 patient-year[2].

There has been no epidemiological assessment to investigate the medical need of reversal in patients undergoing emergency surgery or major bleeding from trauma or fracture receiving NOACs in Japan. The objective of this study is to assess the incidence of emergency surgery and major bleeding associated with fracture and head trauma in Japanese patients prescribed with oral anti-coagulants such as warfarin, dabigatran, apixaban, rivaroxaban and edoxaban.

## **8. RESEARCH QUESTION AND OBJECTIVES**

The primary objective of this study is to assess the incidence rate (overall and age stratified) of emergency surgery and major bleeding associated with fracture and trauma among patients to characterize the incidence of relatively homogeneous population who undergo oral anticoagulants (OAC) therapy.

The secondary objective is to estimate the incidence rate (overall and age stratified) of cardiac tamponade or pericardiocentesis occurring during or within one day after conducting a PCI or cardiac ablation procedure.

## **9. RESEARCH METHODS**

### **9.1 STUDY DESIGN**

#### Study design

- Non-interventional study based on existing health insurance claims data

#### Treatments Considered:

- Dabigatran, rivaroxaban, apixaban, edoxaban, and warfarin

#### Strength of the study design

- Up-to-date epidemiological information can be obtained using large-scale real-world database.

### **9.2 SETTING**

MDV clinical database is used.

#### Inclusion criteria

1. >18 year old non-valvular atrial fibrillation (NVAF) patients
2. Prescribed dabigatran, rivaroxaban, apixaban, edoxaban or warfarin
3. Patients with confirmed date of initiation of OACs
4. Patients with a minimum of 6 months of enrolment data prior to index date
5. Has an index date between 14th of March 2011 to 30 June, 2016

#### Exclusion criteria

1. Patients receiving two or more oral anti-coagulants at the same time at index date
2. Patients with prescriptions of index treatment in the 6 months prior to index date
3. Patients without enrolment period of at least six month in the database

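### Section 9.2's exclusion list omits dialysis/kidney transplant and DVT/PE, which the abstract and Section 9.11 both exclude; flutter and the named valve conditions are excluded in the abstract only

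*Combined protocol and SAP*

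**What the plan says.** Eligibility is described in three places.

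- **Section 9.2 (Setting).** There are three numbered exclusions: "Patients receiving two or more oral anti-coagulants at the same time at index date"; a prescription of the index treatment in the preceding six months; and "Patients without enrolment period of at least six month in the database". Inclusion criterion 1 asks for non-valvular AF without naming conditions or codes.
- **Section 4 (Abstract).** Besides short enrolment, it excludes patients "being dialysis or kidney transplant recipients in baseline period, having either atrial flutter, valvular atrial fibrillation (AF), mechanical valve placement", then "rheumatic AF, and/or mitral valve prolapse/regurge/stenosis in baseline period", and finally those with a record of deep "vein thrombosis or pulmonary embolism < 6months before AF diagnosis in baseline period" (the sentence runs over a page break).
- **Section 9.11 (Subjects).** "The exclusion criteria also include patients on dialysis or kidney transplant and having records of deep vein thrombosis or pulmonary embolism". The stated purpose is "to exclude those patients who are presumed to have high risk of bleeding and those receiving OAC for indications other than atrial fibrillation". On valve disease it says only that the criteria are "intended to select those Japanese atrial fibrillation patients who have non-valvular etiology". Flutter is not mentioned.

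The abstract identifies NVAF by ICD-10 code I48. Section 9.3.3, Table 1 also lists I48 among the codes for the baseline covariate valvular disease. Annexes 1 and 3 both read None, so no separate code list is referenced.

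**The concern.** Section 9.2 is where a programmer would look for the cohort rules, and its list lacks two exclusions that the protocol states twice elsewhere. The study tests no hypothesis and pools all anticoagulants into one group, so its results are incidence rates in a single cohort. Who enters that cohort determines both the event count and the patient-years. Section 9.11 says the omitted patients are removed because they are presumed to bleed more or to take the drug for another indication, and two of the three primary components are major bleeding. Two analysts, one working from 9.2 and one from the abstract, could each follow their section faithfully and report rates for different populations. The quality checks in Section 9.8 name no single eligibility specification against which to catch this.

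**Working it through.** The check is a comparison of text; the plan states no figure to reproduce on this point.

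| Criterion | Abstract | 9.2 | 9.11 |
|---|---|---|---|
| Under six months in the database | excluded | excluded | not stated |
| Dialysis or kidney transplant | excluded, baseline period | **absent** | excluded, no window |
| DVT or PE | excluded, under 6 months before AF diagnosis | **absent** | excluded, no window |
| Atrial flutter | excluded | absent | absent |
| Valvular AF | excluded | general (inclusion 1) | general (intent) |
| Mechanical valve, rheumatic AF, mitral disease | excluded by name | not named | not named |
| Two or more anticoagulants at index | absent | excluded | absent |
| Six-month washout | any anticoagulant | index treatment | new initiators, no window |
| Index window opens | 1 March 2011 | 14 March 2011 | 14 March 2011 |

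**Count.** Taken item by item, the abstract has 8 exclusions: enrolment, dialysis/transplant, flutter, valvular AF, mechanical valve, rheumatic AF, mitral disease and DVT/PE. The 9.2 exclusion list carries 1, leaving 8 − 1 = 7. Those seven are not alike: 2 are restated in 9.11 (dialysis/transplant, DVT/PE), 4 are valvular and partly covered by the non-valvular requirement, and 1 (flutter) is in the abstract alone; 2 + 4 + 1 = 7. None of the seven has an eligibility code. The codes in Table 1 define covariates.

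**Effect on a rate.** Let p be the share of patient-years contributed by the patients in dispute and k the ratio of their event rate to that of the remaining patients. The rate from 9.2 alone, divided by the rate with the exclusions applied, is 1 + p(k − 1). The documents give neither p nor k, so neither size nor direction follows. Section 9.5 does not help. Its total adds up (7,441 + 23,412 + 16,026 + 12,779 + 3,230 = 62,888), but those patients are described only by six months of baseline and no prior anticoagulant. Whether these exclusions had been applied is not stated.

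**Side differences.** From 1 March 2011 to 30 June 2016 inclusive is 1,949 days, and from 14 March it is 1,936. The difference is 13/1,949 = 0.7% of the window. The washout wording could matter only if index treatment meant the single drug and first prescription meant first within the window, and then only for index dates from 14 March to about 13 September 2011. That is 184/1,936 = 9.5% of calendar days, not of patients.

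**Covariate codes.** If I48 both admits a patient and defines valvular disease, the valvular row of the baseline table is positive for essentially everyone whose I48 record falls in the covariate look-back.

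**The case against.** The strongest reply is that the intent is recoverable. Section 9.2 is silent on dialysis/transplant and DVT/PE; it does not admit them. Section 9.11 belongs to the same Research Methods chapter and can be read as adding to the 9.2 list. It agrees with the abstract, and no section says these patients are included. This largely stands. A reader might infer that nothing in the protocol settles whether these patients belong in the cohort, but two sections agree that they do not. What stays open is flutter, the DVT/PE window and the codes.

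A reader might also infer from 1 of 8 that almost the whole exclusion list is lost. That overstates it: four of the seven absent items are valvular, and 9.2 and 9.11 already require non-valvular AF. The general term does not replace the named conditions, however. It does not clearly cover mitral prolapse or regurgitation, and the only NVAF code given is I48.

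The washout difference is largely answered by 9.2 itself, which requires a confirmed date of anticoagulant initiation and defines the index date by the first oral anticoagulant prescription.

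What survives is that 9.2 as written is incomplete against the protocol's own statements, and that merging the sections does not yield one rule: a DVT/PE record within a stated window and a record without one select different patients.

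**Conclusion.** The inconsistency is real and should be fixed. Section 9.2 omits two exclusions that the abstract and 9.11 share. Flutter and the named valve conditions rest on the abstract alone, as does the DVT/PE window, and 9.2's concurrent-anticoagulant exclusion is missing from the abstract. The harm depends on a cohort being built from 9.2 without the other sections; in that case the rates describe a population the protocol says it does not study.

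A reader might infer that the reported rates would be too high, since 9.11 presumes a high bleeding risk. The documents do not support this. They give no event rates for these patients, and part of the stated reason is indication rather than bleeding risk. With size and direction both unknown in a descriptive, pooled study, the point does not support a claim that the results would be invalid. The start-date and washout differences are minor. The I48 overlap is a genuine but separate covariate error; it does not touch eligibility or the rates unless that code list is reused as an exclusion.

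**What to change.** Before analysis, reconcile the abstract, 9.2 and 9.11 into one eligibility list held in 9.2:

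- Enter the dialysis/kidney transplant and DVT/PE exclusions with codes, look-back periods and one stated DVT/PE window.
- State whether the flutter and named valvular exclusions apply, with codes if they do and a reason if they do not.
- Repeat the concurrent-anticoagulant exclusion in the abstract.
- Use one index-window start date for the primary objective, and word the washout as any oral anticoagulant.
- Report the number of patients removed by each criterion.

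Separately, remove I48 from the valvular disease codes in Table 1.

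The cost is protocol wording, code lists and cohort-selection code; no new data are needed. The downside is a somewhat smaller cohort than 9.2 as written would give. Settling the list before any rate is seen also keeps eligibility from becoming a post-hoc choice.
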